Power. This study is powered to estimate the effects of doxazosin on significant reduction in PTSD symptoms at the end of treatment (see Hypothesis 1), and increased abstinence rates at the end of treatment (see Hypothesis 2). Placebo rates of reduction in CAPS scores are conservatively estimated to be 20% (Zohar et al., 2002). In a small pilot study, De Jong et al. (2010) found ~31% reduction in CAPS scores using 4mg doxazosin. A sample of 100 participants will provide 80% power with a .05 type 1 error rate to detect a difference in the reduction of CAPS scores between doxazosin (31±20%) and placebo (20±20%). Placebo rates of drug abstinence are estimated from established double-blind placebo controlled trials. Continuous abstinence from weeks 9-12 is observed in 10-15% of treatment seekers without co-occurring PTSD (Shorter et al., 2013) so we anticipate an attenuated rate of 5-10% in the placebo group. Although there is limited information on the effectiveness of doxazosin in addiction, a sample of 100 subjects (50 in each arm) will provide adequate power to detect an abstinence rate as low as 32% in the doxazosin when the placebo cessation rate is 10% and as low as 23% when the placebo rate is 5%. Due to the nature of the study population, we anticipate ~30% dropout rate; thus the number of subjects randomized is inflated to 144, n=72 randomized to each treatment arm of the study.

Power calculations for the neuroimaging component are based on previous studies of individuals with PTSD or substance use disorders. Based on our previous work and the extant literature, we conservatively estimate that approximately 88/144 will be eligible and volunteer to participate in the neuroimaging component. Of these 88 participants, half (n=44) will be assigned to doxazosin and half to placebo (n=44). Hypotheses 3A and 3B will, therefore, involve the subset of 44 participants who complete the neuroimaging component and receive doxazosin treatment. A recent study of Veterans with PTSD (n=14) as compared to controls (n=15) observed significant differences in PFC-AMY resting state connectivity (Sripada et al., 2012). The effect size for this difference was 0.8 (measured using Cohen's d). Thus, power (1- β) reaches .80 with a total sample size of N=26 (two-tailed, alpha=.05). Another recent study of cocaine-dependent individuals (N=45) found that

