Hypothesis 2: Participants who receive doxazosin, as compared to placebo, will evidence significantly greater reductions in SUD severity. To test this hypothesis, logistic regression analysis will be used to examine rates of abstinence (TLFB, biological tests) during the end of treatment phase (week 9-12). Weekly point prevalence abstinence will be examined using generalized linear models under a generalized estimating equations (GEE) framework. GEE models will allow for examination of differential effects of doxazosin vs. placebo on abstinence over the course of the treatment phase of the study. Weekly abstinence (yes/no) as well as amounts (e.g., standard drink units, dollar amount of substances) will be examined over time to determine if treatment is effective in reducing substance use when abstinence is not achieved.

Hypothesis 3A: PFC-AMY connectivity at rest and in response to trauma vs. neutral cues will predict amount of change in PTSD symptoms (CAPS-5).

Hypothesis 3B: PFC-AMY connectivity at rest and in response to substance vs. neutral cues will predict time to first use of alcohol or drugs (TLFB).

The following preprocessing and analytical parameters will be used to test hypotheses 3A-3B. **Preprocessing:** Post-acquisition preprocessing and statistical analysis of all of imaging data will be performed using FEAT (fMRI Expert Analysis Tool) Version 5.98, part of FSL (FMRIB's Software Library). Data will be preprocessed using scripting tools from FEAT. Non-brain signal will be removed using FSL's BET brain extraction. Scans will be corrected for motion using FSL's linear registration and scans will be spatially smoothed using a Gaussian kernel of 8 mm FWHM. Participants with head motion ≥ 0.2 mm will be excluded from the analyses [1]. Motion artifacts will be identified and scrubbed from each subject's data. Scans will be spatially co-registered with a standardized anatomical template (Montreal Neurological Institute) using a 12 parameter affine transformation.

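### Hypothesis 2 does not name its test, and at a 5% placebo abstinence rate neither usual test from ordinary logistic regression keeps both power and type I error near target

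*Combined protocol and SAP*

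**What the plan says.** The Assessment Instruments section makes substance use severity on the TLFB one of two primary clinical outcomes, and the Power section sizes the trial on abstinence as well as on CAPS.

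For placebo, the Power section states "we anticipate an attenuated rate of 5-10% in the placebo group". It then says that "a sample of 100 subjects (50 in each arm) will provide adequate power". Two scenarios are attached to this claim. The first is "an abstinence rate as low as 32% in the doxazosin when the placebo cessation rate is 10" per cent. The second, again for doxazosin, is a rate "as low as 23% when the placebo rate is 5" per cent. For abstinence it gives no power figure, significance level, sidedness or test. The neighbouring CAPS sentence does give a target: "A sample of 100 participants will provide 80% power with a .05 type 1 error rate". Sidedness appears only in the imaging calculation ("two-tailed, alpha=.05").

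For the analysis, Hypothesis 2 says that "logistic regression analysis will be used to examine rates of abstinence (TLFB, biological tests) during the end of treatment phase (week 9-12"). It does not say whether the treatment effect is judged by a Wald, likelihood-ratio, score or penalised test, and it has no rule for an arm with no abstainers. The General paragraph of Statistical Analyses puts all analyses on everyone randomized. The Power section explains that number: "we anticipate ~30% dropout rate; thus the number of subjects randomized is inflated to 144", or 72 per arm.

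**The concern.** A placebo rate of 5-10% means 2.5 to 5 expected abstainers of 50. With so few events, tests that agree in large samples diverge. The coefficient p-value usually reported from logistic regression is a Wald p-value, which becomes very conservative here. It cannot reject at all when an arm has no abstainers, because the odds ratio estimate is then infinite. The likelihood-ratio test from the same fit errs the other way and rejects too often under the null.

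The stake is one of the two primary comparisons. Depending on a choice the plan leaves open, it either loses power against the plan's own scenario or exceeds its nominal error rate. An unnamed test can also be chosen after the data are seen.

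**Working it through.** **Inputs.** From the Power section: 50 per arm; rates of 5% vs 23% and 10% vs 32%; about 30% dropout; 72 per arm randomized. Assumed for abstinence: 80% target and alpha 0.05 (borrowed from the CAPS sentence), two-sided testing (borrowed from the imaging calculation), and an unadjusted comparison of two proportions, since Hypothesis 2 lists no covariates.

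**Dropout check.** 100 / 0.7 = 142.9, so 143; 144 in two equal arms is consistent.

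**Method.** With a placebo and b doxazosin abstainers, exact power = sum over all (a, b) of Bin(a; n, pP) × Bin(b; n, pD) × 1[test rejects]. Type I error is the same sum with pP = pD. For Wald, samples with an empty cell count as not significant.

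**The plan's own claim.** At 50 per arm, 23% vs 5% gives 78.9% (score, i.e. Pearson chi-square), 79.4% (likelihood ratio) and 78.4% (arcsine formula). For 32% vs 10% the figures are 80.0%, 80.0% and 79.8%. Reading the claim as about 80% is therefore reasonable, and it reproduces. It does not reproduce under every method: the pooled normal formula gives 74.4% and 77.9%, and Fisher's exact test 66.1% and 72.1%.

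**Comparison of tests, 50 per arm.**

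| Test | Power 5% vs 23% | Power 10% vs 32% | Type I error, both 5% | Type I error, both 10% |
|---|---|---|---|---|
| Wald | 66.4% | 77.0% | 0.2% | 2.4% |
| Likelihood ratio | 79.4% | 80.0% | 8.8% | 6.1% |
| Score | 78.9% | 80.0% | 4.3% | 5.1% |
| Firth, penalised likelihood ratio | 77.1% | 79.3% | 4.3% | 4.8% |
| Firth, Wald | 70.8% | 77.2% | 0.2% | 2.1% |

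**Hand check of the Wald figure.** Log odds ratio = ln(0.23/0.77) − ln(0.05/0.95) = −1.208 + 2.944 = 1.736. Its standard error from expected counts = √(1/2.5 + 1/47.5 + 1/11.5 + 1/38.5) = √0.534 = 0.731. Then 1.736/0.731 − 1.960 = 0.416, and Φ(0.416) = 66.1%, against 66.4% by enumeration.

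**No placebo abstainers.** At 50 per arm the probability is 0.95^50 = 7.7% at a 5% rate and 0.90^50 = 0.5% at 10%. At 72 per arm and 5% it is 0.95^72 = 2.5%.

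Two such tables show how the tests part:
- 0 vs 4 abstainers of 50: the score statistic is 100 × (50 × 4)² / (50 × 50 × 4 × 96) = 4.17, above 3.84, so it rejects. Wald cannot.
- 0 vs 3: the score statistic is 100 × (50 × 3)² / (50 × 50 × 3 × 97) = 3.09, not significant. The likelihood-ratio statistic is 2 × [3 ln 0.06 + 47 ln 0.94 − 3 ln 0.03 − 97 ln 0.97] = 4.25, which rejects. Tables like this drive its inflated error.

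**All 72 per arm analysed, 5% vs 23%.**
- Same rates in everyone: Wald 86.5%, score 90.7%, Firth penalised likelihood ratio 90.6%.
- The 22 dropouts per arm counted as non-abstinent (rates 5% × 50/72 = 3.5% and 23% × 50/72 = 16.0%): Wald 62.2%, score about 76%, Firth penalised likelihood ratio 74.3%.

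**The case against.** A reader might infer that the trial is underpowered for abstinence, or that its power statement is wrong. The documents do not support that. Wald is nowhere named, and the planning figures reproduce near 80% with a score test and also with the likelihood-ratio test from an ordinary logistic fit. What the plan lacks is a stated test. That part of the objection stands, as do these limits:

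- The large loss belongs to the bottom of the placebo range. At 10% vs 32% Wald gives up 3 points.
- The 66% treats every empty-cell sample as not significant. If those samples were judged by likelihood ratio, power would be 74.1%. An empty cell removes the ordinary odds ratio estimate, not every means of testing.
- The 80% benchmark comes from the CAPS sentence, not the abstinence one.
- The stated analysis set is 72 per arm, and the Missing Data paragraph plans imputation when more than 10% is missing. Wald power then lies anywhere from 62% to 86%, depending on how dropouts are handled. That spread exceeds the gap between tests.

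The objection does not dispose of the point. In both 72-per-arm cases Wald still trails the score test, by about 4 and 14 points. The likelihood-ratio test reaches its power at 5% partly by rejecting too often: 8.8% at 50 per arm, and still above 7% at 72. So neither usual test from the ordinary fit is a satisfactory default at the low end of the plan's own range.

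**Conclusion.** The point holds as a fault in the choice and specification of the analysis, not as a fault in the sample size. At 50 per arm and 23% vs 5%, a Wald test costs about 11 to 13 points of power relative to Firth with penalised likelihood-ratio inference (77.1 − 66.4 = 10.7) or the score test (78.9 − 66.4 = 12.5), and its type I error is 0.2%. The likelihood-ratio test keeps the power but has 8.8% type I error at a common 5% rate. Score and Firth penalised likelihood-ratio tests both hold type I error at 4.3% there. At 32% vs 10% the differences are small. The stronger conclusion, that the power claim fails, would require the plan to have committed to Wald inference, and it has not.

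This rests on two-sided 0.05, an 80% reading of the unquantified claim, an unadjusted comparison and 50 evaluable per arm, with the 72-per-arm cases as bounds. Firth fitting helps only with penalised-likelihood inference: paired with Wald p-values it gives 70.8%.

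**What to change.** In Hypothesis 2, name the treatment-effect test for week 9-12 abstinence. Use either Firth-penalised logistic regression with penalised likelihood-ratio (not Wald) p-values and confidence intervals, or the score test. Firth gives a finite odds ratio when an arm has no abstainers. If the score test is chosen, add a sentence on how the effect and interval will be reported in that case.

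In the Power section, name the same test and give its power at 50 per arm, two-sided 0.05: about 79-80% for 32% vs 10% and 77-79% for 23% vs 5%.

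These figures are for unstratified tests. A Cochran-Mantel-Haenszel test over the four randomization strata is a natural form of the score test, but its power was not computed here and should be before a figure is quoted for it.

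The cost is SAP wording and a standard software option, with no new data or participants. The stated power will be slightly under 80%.

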Neuroimaging Component. Given the severe negative outcomes associated with co-occurring PTSD and AUD, investigating potential neural circuitry underlying PTSD/SUD as well as neural circuitry involved in positive therapeutic response to doxazosin could be important in guiding future studies targeting this circuitry using other therapeutic agents or treatment modalities. To that end, fMRI data will be acquired at baseline and end-of-treatment on all eligible participants to examine (a) resting state connectivity, and (b) response to trauma, substance, and neutral cues. We will continue to work closely with the CAP Co-Is and Neuroimaging Core, directed by [name], to ensure comparability of imaging data acquisition and pre-processing. Scans will be conducted at the MUSC Center for Biomedical Imaging (CBI), which houses a Siemens 3T TIM Trio MRI scanner (Siemens Medical, Erlangen, Germany). The neuroimaging component will involve three visits, each lasting 60-90 minutes and following the same procedures. In visit 1, imagery scripts will be developed according to standardized procedures described by Sinha (Sinha & Li, 2007) and employed in our ongoing research with Veterans. During visits 2 and 3 (see Fig 5), participants will first be screened for metal using a handheld metal detector. Trained staff will position subjects on the scanner bed with foam padding placed around their head to prevent motion. Participants will wear headphones to listen to the audio-recorded scripts. For co-registration and normalization of functional images, a high resolution T1-weighted MPRAGE anatomical image will be acquired with the following parameters: TR = 2100 ms, TE = 4.18 ms, flip angle = 12°, field of view = 256 mm, slice thickness 1.0 mm. The scanning planes will be oriented parallel to the anterior commissure-posterior commissure line. Next, participants will be asked to relax and keep their eyes opened and fixed on a cross-hair for six-minutes while resting state data are collected.

Following the resting state scan, participants will be exposed to trauma, substance and neutral cues. Resting state scans will always occur before trauma and substance cue runs (Fig. 5). We will use a block design

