consisting of one 12-minute run. During the trauma cue, participants will hear an audio recording describing their traumatic event. During the blocks of neutral cue, participants will hear an audio recording describing their relaxing scenario. During the substance cue, participants will hear an audio recording describing in detail the last time they consumed alcohol or drugs. To minimize potential carry-over effects, the runs will be counterbalanced so that half of the participants in the placebo group and half of the participants in the treatment group are exposed to the trauma cue first and the remaining participants in each group are exposed to the substance cue first. T2*-weighted gradient-echo planar images (EPI) will be acquired with the following parameters: TR = 2000 ms, TE = 27 ms, flip angle = 76°, matrix 64 x 64, field of view = 23 cm, slice thickness = 3.7 mm with no gap, with 36 slices to cover the entire brain.

[figure not shown]

Fig 5. Overview of fMRI neuroimaging session. Assessment of (a) resting state connectivity, and (b) response to trauma, alcohol and neutral cues.

Statistical Analyses

General. Baseline clinical and demographic characteristics will be collected and contrasts performed between treatment groups. Continuous and ordinal characteristics will be compared using a Wilcoxon Rank-Sum test statistic while categorical characteristics will be compared using a Pearson Chi-Square test statistic. All analyses will be performed on the intent-to-treat sample consisting of all randomized subjects.

Randomization. The randomization will be stratified by (1) PTSD severity (PCL total score) and (2) AUD severity (AUDIT total score) for a total of four strata. Urn randomization will be employed to balance the randomization assignment with respect to these strata. The purpose of stratification is to distribute these potential prognostic factors equally across treatment groups. To the extent that the stratification variable is predictive, stratifying on it may enhance statistical power to identify treatment effects.

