fMRI Analysis: Functional connectivity will be measured using a PPI seed-based approach [2]. PPI analyses for resting state, trauma and substance cues will be performed separately. Customized sq. wave forms representing the trauma run (1=trauma block and -1=neutral block) and the substance cue run (1=substance block and -1=neutral block) the duration of each block will be convolved with a double-gamma hemodynamic response function. A mask of the seed region will be made using a 12-mm diameter sphere located in the center

of the amygdala using the MNI coordinates (x, y, z = ±22, 0, -22). The transformation parameters described above will also be applied to the mask. For each subject, the mean corrected and high pass filtered time series of the BOLD signal in the AMY will be extracted and used in a single subject whole brain PPI analysis. The PPI model will include the task vector, time series of the BOLD signal in the AMY, a term representing the positive task x seed interaction, and a term representing the negative task x seed interaction. The first level analysis will generate contrast images of the parameter estimates for each of the four regressors. Voxels will be thresholded at $Z>2.3$ using a corrected cluster threshold of $p=0.05$. The contrast images of the parameter estimates of the positive and negative task x seed interactions will be combined for group-level t-tests to identify regions that exhibited altered connectivity with the AMY during the trauma and substance cues as compared to neutral cues. All group-level results will be thresholded at $Z>2.3$ using a corrected cluster threshold of $p=0.05$. Separate linear regression tests will be used to test for associations between PFC-AMY connectivity at baseline and improvement in PTSD and SUD symptoms during treatment. Changes in CAPS-5 total scores will be regressed against the parameter estimate obtained from the center voxel from each cluster that exhibited a significant task x seed interaction with the AMY at rest and in response to the trauma cue (Hypothesis 3A). The number of days to first use (TLFB) will be regressed against the parameter estimate obtained from the center voxel from each cluster that exhibited a significant task x seed interaction with the AMY at rest and in response to the substance cues (Hypothesis 3B).

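### The power section limits Hypotheses 3A and 3B to the 44 scanned doxazosin participants without a reason, against the plan's own all-randomized rule; a one-arm slope cannot separate response to doxazosin from prognosis

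*Combined protocol and SAP*

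**What the plan says.** Statistical Analyses, Power, expects about 88 of the 144 randomized participants to be scanned, of whom "half (n=44) will be assigned to doxazosin and half to placebo (n=44"). The next sentence reads: "Hypotheses 3A and 3B will, therefore, involve the subset of 44 participants who complete the neuroimaging component and receive doxazosin treatment". The split accounts for the number 44. It does not say why the placebo half is left out.

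Other parts of the document read differently:

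- **General** (same chapter) puts all analyses on the intent-to-treat sample of all randomized subjects.
- **Neuroimaging Component** says that "fMRI data will be acquired at baseline and end-of-treatment on all eligible participants". It counterbalances cue order across "half of the participants in the placebo group and half of the participants in the treatment group", so placebo participants have the same scans.
- **Hypothesis 3A** says connectivity "will predict amount of change in PTSD symptoms (CAPS-5"); 3B says it will predict time to first use. Neither names an arm.
- **fMRI Analysis** plans separate linear regressions of outcome on baseline connectivity, one per significant cluster. It has no arm restriction, treatment term, connectivity-by-treatment term or baseline CAPS-5.

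On purpose, the Neuroimaging Component says that "neural circuitry involved in positive therapeutic response to doxazosin could be important in guiding future studies". Problems and Alternative Strategies makes imaging a secondary objective that includes circuitry of positive treatment response. The opening Overview speaks of diagnostic and prognostic indicators.

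**The concern.** Two things are at stake.

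1. **The analysis set is not settled.** An analyst following the Power section would use at most 44 participants. One following General and fMRI Analysis would use up to 88. That choice should not be left until the data are in hand.

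2. **The one-arm slope does not serve one of the stated aims.** Connectivity may predict improvement for reasons unrelated to the drug, such as natural course or the behavioral therapy that the plan offers regardless of arm. The slope among doxazosin participants then looks the same as if connectivity marked response to doxazosin. Only the placebo arm can tell these apart, and the planned analysis would discard it. Because the imaging is meant to guide later studies, a result misread as drug response would carry forward.

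If the aim is purely prognostic, the restriction is still unexplained, and it halves the sample.

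**Working it through.** **The plan's figures.** 88/2 = 44 reproduces. The section's two sample-size statements concern two-group differences (d = 0.8 and 1.0), not a slope. For d = 1.0 the total of 34 reproduces (17 per group, two-sided t test). For d = 0.8 the calculation gives 26 per group, 52 in total, not 26 in total; that is a separate matter. The plan gives no correlation between connectivity and outcome.

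**Assumptions (3A only, one predictor, two-sided alpha 0.05).** The correlation r between connectivity and CAPS-5 improvement, given baseline, is 0.30, 0.37 or 0.45. The last two are close to the plan's own d values under r = d/√(d²+4): 0.8/√4.64 = 0.371 and 1.0/√5 = 0.447. The baseline-to-follow-up correlation is 0.5, connectivity is unrelated to baseline (except in step 4), and there are 44 per arm. Scores are standardized.

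**Step 1: doxazosin-only slope, adjusted for baseline.** Fisher z: power = Φ(atanh(r)·√(n−3) − 1.96). At r = 0.37: 0.388 × √41 − 1.96 = 0.53, power 0.70. Over the three values: 0.51/0.70/0.87.

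**Step 2: the same slope unadjusted, as fMRI Analysis plans.** Improvement = baseline − follow-up = 0.5·baseline − e, with var(e) = 0.75, so var(improvement) = 0.25 + 0.75 = 1. The raw correlation is r·√0.75 = 0.260/0.320/0.390. The same formula gives 0.40/0.57/0.75; simulation gives about 0.40/0.57/0.76.

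Both steps use doxazosin data alone, so the results are identical whatever happens on placebo.

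**Step 3: difference in slopes between arms.** The standard error on the z scale is √(2/41) = 0.221. At r = 0.37 on doxazosin and 0 on placebo: 0.388/0.221 − 1.96 = −0.20, power 0.42 (simulation 0.41).

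| Truth | Doxazosin slope, unadjusted | Doxazosin slope, adjusted | Interaction |
|---|---|---|---|
| Same slope in both arms | 40/57/76% | 51/70/87% | 5% |
| Slope on doxazosin only | 40/57/76% | 51/70/87% | 28/41/57% |

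The 95% CI for the slope difference is about ±0.42 SD of improvement per SD of connectivity. Head motion of at least "0.2 mm will be excluded from the analyses", and the plan expects about 30% dropout. If 30% are lost (44 × 0.7 ≈ 31 per arm), interaction power at r = 0.37 v 0 is about 0.30 and the CI about ±0.52.

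**Step 4: why 3A needs baseline CAPS-5.** Suppose connectivity has no effect beyond baseline severity and correlates 0.2/0.3/0.4 with it (assumed). The raw correlation with improvement is 0.5 times that: 0.10/0.15/0.20. The unadjusted doxazosin-only slope is then significant in about 10/16/26% of trials, and in 5% once adjusted.

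**Step 5: the purely prognostic reading.** The detectable r at 80% power is tanh(2.80/√(n−3)): 0.41 with 44 and 0.295 with 88. The gain holds only if both arms share the slope.

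**The case against.** The strongest reply is that no stated hypothesis is tested invalidly. 3A and 3B say only that connectivity predicts outcome, and a doxazosin-arm slope tests that. **This stands.** The 40/57/76% with equal slopes are not false-positive rates for 3A; they are ordinary power to find a true association. A reader might infer that the planned test is invalid or that its type I error is inflated. Apart from the baseline-severity problem in step 4, the documents do not support that. The fault lies in reading the result as response to doxazosin.

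A second reply is that the aim in the Neuroimaging Component explains the restriction. It may, but the text does not say so, and that aim is the one that needs the placebo contrast.

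Third, the interaction has low power and will usually not establish specificity. **This stands**, and it is why the interaction should be reported as an estimate with a CI and should not decide 3A or 3B.

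Fourth, one might infer that moving to a two-arm model costs nothing. That holds only if residual variance is equal in the arms. In simulation at r = 0.37 v 0, if the placebo residual SD is 1.3 times larger (assumed), power for the doxazosin slope from a pooled-variance model falls to 0.57, against 0.70. If the doxazosin SD is the larger by that factor, a null doxazosin slope rejects in 7.4% of trials. **This stands**, so a pooled-variance model should not decide 3A and 3B.

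**Conclusion.** The concern holds within limits. The restriction has no stated reason and conflicts with the General paragraph and with analysis text that names no arm. The doxazosin-only slope is adequate for prediction. It cannot show that connectivity marks response to doxazosin, since it gives the same 40/57/76% (unadjusted) or 51/70/87% (adjusted) under both explanations.

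These figures rest on assumed correlations, a baseline-to-follow-up correlation of 0.5, 44 per arm and a single predictor. A multiplicity correction across clusters would lower power. They apply to 3A and not directly to 3B.

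The objective is secondary and hypothesis-generating, and Hypotheses 1 and 2 are untouched. This is a cheap improvement that should be made before the imaging data are analyzed.

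**What to change.** Reconcile the General, Power and fMRI Analysis text as follows:

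- **Analysis set.** 3A and 3B use all randomized participants with a usable baseline scan, by assigned arm (at most about 44 per arm before head-motion exclusion and dropout).
- **Clusters.** The group-level step, in which contrast images "will be combined for group-level t-tests to identify regions that exhibited altered connectivity with the AMY", uses both arms together on the pre-treatment scan.
- **Model.** Estimate the connectivity slope separately in each arm, or in a two-arm model with arm-specific residual variance or robust standard errors. Adjust 3A for baseline CAPS-5.
- **Decision.** The doxazosin-arm slope remains the test of 3A and 3B.
- **Reporting.** Give the placebo-arm slope beside it, and the between-arm difference in slopes (connectivity by treatment) with its 95% CI. Label that difference exploratory and treat it as the only evidence of doxazosin specificity. Without it, describe a doxazosin-arm finding as prediction, not as response to doxazosin.

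**Cost.** No new scans, visits or participants are needed; the change is revised wording and some extra analysis. Two downsides should be stated in the plan. The interaction is imprecise (power about 0.41 at r = 0.37 v 0, about 0.30 with 31 per arm). The doxazosin slope is also not identical to the one now planned, because the baseline adjustment, the cluster-defining set and the participant set (usable baseline scan instead of completed imaging) all change. How 3B handles participants with no use is a separate matter, not addressed here.

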individuals who relapsed (n=24) during treatment had significantly lower PFC-AMY connectivity at baseline as compared to individuals who did not relapse (n=21) (McHugh et al., 2014). The effect size for this reduction was 1.0. Thus, power (1- β) reaches .80 with only 34 total participants (two-tailed, alpha=.05). The present study is therefore well-powered to test the proposed hypotheses.

Missing Data. We will perform attrition analyses on whether participants and dropouts differ on key variables, and whether variables on which they differ interact with treatment to affect outcome measures. As participants will be randomized to treatment, it is unlikely that missing data will produce biased estimates of treatment effect, as observed and unobserved covariates should theoretically be balanced across treatment groups. In addition, in general, less than 10% missing data have little impact on power and do not introduce bias, regardless of the missing data mechanism. Larger proportions of data missing at random (MAR) or missing not at random (MNAR) could potentially bias study findings and reduce power. If the percent missing data are greater than 10%, propensity score methods will be used for data imputation. In the propensity score method, first the distribution of the missing indicator variable given the observed data is modeled to derive a propensity score. Then observations are grouped on these propensity scores and an approximate Bayesian bootstrap imputation is applied to each group.

Hypotheses. The hypotheses and statistical approaches for testing each hypothesis are listed below. An experienced biostatistician at MUSC ([name], Department of Public Health) who has worked with our group for the past five years will collaborate with [name] (Director of the CAP Data Management and Biostatistics Core) as needed during the project to ensure consistency across sites with regard to scoring and analysis of dependent measures.

Hypothesis 1: Participants who receive doxazosin, as compared to placebo, will evidence significantly greater reductions in PTSD severity. To test this hypothesis, generalized linear mixed effects models will be employed to assess reduction in CAPS-5 and PCL-5 total scores during the treatment phase. Restricted maximum likelihood (REML) methods will be used to estimate the fixed effects and variance components, and model based treatment effect estimates will be used to construct group level tests over time.

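### The imaging power statement counts 44 doxazosin-arm volunteers as 44 completers, with no allowance for the plan's own ~30% dropout or its head-motion exclusion, and the figure of 26 that might cover 3A is a per-group number

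*Combined protocol and SAP*

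**What the plan says.** All of this is in the combined protocol and SAP, mostly under Statistical Analyses, Power.

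- **Main trial.** The plan states "Due to the nature of the study population, we anticipate ~30% dropout rate" and raises the number randomized from 100 to 144 for that reason.
- **Imaging sample.** It estimates that "approximately 88/144 will be eligible and volunteer to participate in the neuroimaging component", assigns half (44) to each arm, and concludes that "Hypotheses 3A and 3B will, therefore, involve the subset of 44 participants who complete the neuroimaging component and receive doxazosin treatment".
- **Benchmarks.** A PTSD-versus-control comparison with d = 0.8 is said to need 26 participants in total for 80% power. A relapse-versus-no-relapse comparison follows: "The effect size for this reduction was 1.0", so that power "reaches .80 with only 34 total participants (two-tailed, alpha=.05"). The paragraph ends: "The present study is therefore well-powered to test the proposed hypotheses".
- **Further loss.** The preprocessing text for Hypotheses 3A and 3B adds: "Participants with head motion ≥ 0.2 mm will be excluded from the analyses". No expected rate is given.
- **Planned tests.** The fMRI Analysis text regresses CAPS-5 change (3A) or days to first use (3B) on baseline connectivity, using linear regression.

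**The concern.** The same 44 people are described first as volunteers, then as assigned to doxazosin, then as completers, so the implied loss is zero. The 88 cannot easily be read as already net of dropout. Its denominator is the 144 randomized, its conditions are eligibility and willingness, and assignment is mentioned only afterwards. One paragraph earlier the plan expects to lose about three in ten of the same population.

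The imaging hypotheses are the stated secondary objective. If the evaluable number is overstated, a null regression in one arm could be read as evidence against the biomarker when the study had limited ability to detect it. The primary efficacy tests (Hypotheses 1 and 2) are sized separately and are not affected.

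**Working it through.** **Inputs from the Power section:** 88 imaging volunteers of 144 randomized; 44 in the doxazosin arm; about 30% dropout; two-sided alpha 0.05; power 0.80; effect sizes 1.0 (34 in total) and 0.8 (26 in total). The motion-exclusion rate is not given.

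**1. Reproduce the plan's figures** (two-sample t-test, equal groups, noncentral t).
- d = 1.0: n = 16.7 per group, so 17 per group and 34 in total; power 0.807. The stated 34 reproduces exactly.
- d = 0.8: n = 25.5 per group, so 26 per group and 52 in total. The stated total of 26 does not reproduce. The normal approximation gives 25 per group, a one-sided test 21 per group, and a paired test 15. None gives a total of 26. Power at 26 in total is 0.50. The stated number matches the per-group requirement.

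**2. Apply the plan's dropout rate to the imaging arm.**
- 44 × (1 − 0.30) = 30.8, about 31. Using 100/144 instead, 44 × 100/144 = 30.6.
- Loss at which 34 is no longer met: 1 − 34/44 = 22.7%.
- Volunteers needed in the arm to keep 34 at 30% loss: 34/0.70 = 48.6, so 49.

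**3. Power in the plan's own two-group framework.**

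| Evaluable in doxazosin arm | d = 1.0 | d = 0.8 |
|---|---|---|
| 44 (no loss) | 0.900 | 0.736 |
| 34 | 0.807 | 0.619 |
| 31 (30% loss) | 0.767 | 0.576 |
| 28 (30% dropout, then 10% motion loss) | 0.721 | 0.531 |

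The 10% motion loss in the last row is my assumption: 44 × 0.70 × 0.90 = 27.7. With the 24:21 split of the cited relapse study, power at 31 and d = 1.0 is 0.764. The normal approximation gives 0.795.

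**4. Power for the analysis actually planned.** Hypotheses 3A and 3B are regressions within one arm, not two-group comparisons. By Fisher's z, the smallest correlation detectable with 80% power is |r| = tanh[(1.960 + 0.842)/√(n − 3)].
- n = 44: tanh(2.802/√41) = 0.412.
- n = 31: tanh(2.802/√28) = 0.485.

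**The case against.** The strongest reply is that dropout from the trial is not the same as loss from these analyses.

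- **Predictor.** It is connectivity at baseline, so a missed week-12 scan does not by itself remove anyone.
- **Outcome.** Table 1 schedules CAPS-5 at week 6 as well as week 12, and TLFB throughout treatment. A dropout may therefore have a change score or an observed first use.
- **Analysis rules.** The General paragraph calls for analysis of all randomized participants, and the Missing Data paragraph for imputation when more than 10% of data are missing.
- **Size.** The inputs are rounded, the plan calls its volunteer estimate conservative, and the gap at d = 1.0 is 3 people, or 77% against 80%.

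Much of this stands. It makes 31 a scenario and not a forecast. If at least 34 of the 44 (77%) supply usable data, the relapse benchmark is met.

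It does not rescue the text as written. The plan itself defines the 3A/3B set as those who complete the component, and the Neuroimaging Component section includes an end-of-treatment scan in it. Nothing says that a week-6 CAPS-5 will stand in for week 12, or how days to first use is set for someone who leaves without using. Imputation does not restore the lost information, and the Missing Data paragraph accepts that larger proportions missing can reduce power. Motion exclusion works in the other direction. If half the dropouts contributed (my assumption), 44 × 0.85 = 37.4 would remain, and motion loss above 1 − 34/37.4 = 9% would again go below 34.

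A reader might also infer that the plan's own figures show both hypotheses to be short of participants through dropout. They do not: 34 belongs to the relapse comparison, closest to 3B, and 31 still exceeds the stated 26, which is closest to 3A. The difficulty for 3A is that 26 is itself wrong as a total.

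**Conclusion.** The point holds in a limited form. The imaging sample carries neither the plan's dropout rate nor its motion exclusion, and the conclusion that it is well-powered does not follow from the figures given.

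- **3B (benchmark 34, d = 1.0).** If the full 30% is lost, about 31 remain and power is about 77%, against 90% at 44. The benchmark is missed once total loss exceeds 22.7%. This is a narrow shortfall.
- **3A (benchmark 26, d = 0.8).** The correct total is 52, which even 44 does not reach. Power is 0.74 at 44 and 0.58 at 31. Here the mislabelled requirement matters before any dropout.

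The power figures assume near-equal groups and the plan's effect sizes. The count of 31 assumes that every dropout is lost and that nobody is excluded for motion. The documents do not support reading 31 as the number that will be analysed. Nor do they support easing the shortfall by pooling the arms, because the Power section confines 3A and 3B to participants receiving doxazosin.

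**What to change.** In the neuroimaging part of the Power section:

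1. Replace the description of 44 completers with the expected number in the doxazosin arm who have a usable baseline scan and an outcome, after dropout and motion exclusion. This is 44 at most, and about 31 at the plan's dropout rate before motion loss. State the motion-exclusion rate assumed, and label these numbers as assumptions.
2. Correct the requirement at d = 0.8 from 26 to 52 in total (26 per group).
3. Replace the well-powered statement with the smallest correlation detectable with 80% power in the planned single-arm regression: |r| about 0.41 at 44 and about 0.48 to 0.49 at 31.

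The cost is wording only. No participants, visits or procedures change. The stated power becomes less favourable.
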